12.1. Prohibited Concomitant Medications/Therapies

During the ‘concomitant’ period of the study (as above), patients may not receive other additional investigational drugs, agents, devices, chemotherapy, or any other therapies that may be active against cancer. While systemic corticosteroid therapy will interfere with the mechanism of action of the study drugs, its use is recommended in some settings. See Protocol Section 6.2.3 for further details.

Medications/therapies that are prohibited will be flagged in the listing of concomitant medications. These will be identified using a medically-approved list of Preferred Names provided by the Sponsor. See [APPENDIX 2](#) for handling of partial dates for concomitant alternative cancer therapies under Algorithm for Prior / Concomitant Medications.

13. Study Drug Exposure

All information relevant to exposure will be calculated from Rollover Cycle 1 Dose 1 (RC1D1), unless otherwise noted. Number of cycles, duration of dose on rollover study in days, duration of dose from first parent study in days, total actual dose received in rollover, dose intensity in rollover, relative dose intensity will be summarized for IMCgp100. Tolerability of study treatment will be assessed by summarizing the number of treatment dose interruptions. Reasons for dose interruptions will be listed.

The SAF analysis set will be used for presenting all exposure and tolerability variables.

13.1. Study Drug Exposure Derivations

A cycle is defined as 28 days = 4 weeks, and at least 1 dose administration visit per cycle for each of the treatment regimen for IMCgp100 (doses are given every week).

The following will be derived:

- *Number of cycles started* = total number of cycles of study drug received (including partial cycles), during the rollover study
- *Number of cycles completed* = total number of complete cycles of study drug received without any interruption, during the rollover study
- *Total planned dose* = sum of the total dose levels that a patient planned to receive during the rollover study, up to the date of last study drug administration
- *Duration of treatment (days)* = (date of last study drug administration – date of first study drug administration in the rollover study + 1). Note that this calculation does not include any post dose rest period. *Duration of treatment from first parent study dose (days)* = (date of last study drug administration – date of first parent study dose of IMCgp100 + 1). Note that this calculation does not include any post dose rest period
- *Duration of interruption (days)* = (start date of next study drug administration following interruption - date of visit in which interruption started). Note that this is calculated for each interruption a given patient has and is only calculated where study drug administration restarts following interruption.
 - “Date of visit in which interruption started” = ‘date of visit’ from the *Date of Visit* eCRF pages, where the visit may also be a visit classified as “not done”. If it is clear that an interruption to dosing has occurred, but no *Date of Visit* eCRF page nor *Administration of Study Drug* eCRF page is entered at least 14 days (i.e. at least 7 days ± 7 day visit window) following the previous dosing visit, where dosing would have been expected, then the date of the *expected* next dose following last administered dose, may be used instead (=previous ‘start date of study drug administration’ + 14 days). See the definition of a *dose interruption* below.
 - If a patient does not have a “start date of *next* study drug administration following interruption” then a dose interruption is not counted because either:
 - The Date of study drug discontinuation from the *End of Treatment* page of the eCRF is filled out, in which case the study drug was discontinued rather than interrupted, or
 - The outcome (interruption or discontinued) is unknown at the time of data cut off, where the study drug discontinuation from the *End of Treatment* page is missing and study drug administration remains skipped or omitted. In this case, it is assumed there was no interruption, until there

is evidence of the study drug administration restarting.

- *Total actual dose received* = sum of the total dose levels that a patient received during the rollover study, up to the date of last study drug administration. The same considerations as for *Total planned dose* above apply here.
- Dose intensity (dose per week) = $[\text{Total actual dose received} / \text{Duration of treatment (days)}] \times 7$
- Planned dose intensity (dose per week) = $[\text{Total planned dose} / \text{Duration of treatment (days)}] \times 7$
- Relative dose intensity (%) = $(\text{Dose intensity} / \text{Planned dose intensity}) \times 100$

Additional Notes on Derivations:

- a. The *Administration of Study Drug* eCRF page will be used for these calculations, unless otherwise noted.
- b. The *number of cycles started* is counted for all cycles of dosing in which study drug was actually administered. Any administration of study drug received, regardless of the 'Actual dose administered' on the eCRF (any dose > 0 units), that occurs in a given cycle (as indicated by the visit) will be counted as one cycle of that study drug.
 - a. Note: Multiple doses within a Cycle do not count multiple times towards the *number of cycles*. For example, four doses (> 0 units) of IMCgp100 during visits in Cycle 1 count as one cycle of study drug since all these dose administrations occurred during a single Cycle (i.e. Cycle 1).
- c. The number of cycles completed is counted for all cycles of dosing in which study drug was actually administered, and furthermore where no interruption occurs. Therefore, in a 4-week cycle, all doses each week must be administered for the entirety of the cycle, in order to count. Reduced doses are allowed, as per number of cycles started above.
- d. The *total planned dose* is based on either the 'Parent Study Dose IMCgp100', or if applicable, the dose entered in 'Was dose changed from parent study' item, on the *Parent Study Details -IMCgp100* eCRF page. This planned dose is summed up over all visits where a patient planned to receive study drug, even if the said dose is actually missed during the visit, up until the cut-off as described above. This calculation is necessary for the planned dose intensity, which is used to calculate the relative dose intensity.
- e. The *total actual dose received* is based on the 'Actual dose administered' entered on the *Administration of Study Drug* eCRF for each visit administration of study drug. The actual dose administered is summed up over all visits where a patient actually received study drug, up until the cut-off as described above.
- f. The date of first study drug administration is taken from the earliest 'Dose start date' entered on the eCRF.
- g. The date of last study drug administration is taken from the latest 'Dose end date'

entered on the eCRF.

Definitions of Dose Interruption:

Dose interruption – an entire dosing visit is skipped or entered as omitted in the eCRF. To clarify, if a dose on a single day is restarted and partial or entire dose is still taken, then this is not a dose interruption. Dose interruptions will be flagged on the *Administration of Study Drug* eCRF page where the response to ‘*Did the patient receive investigational product at this visit?*’ is equal to ‘*No, reason for dose omission*’. Also, dose interruptions are counted in cases where a patient misses an entire study visit, where dosing is expected.

A single interruption is defined as any length of time a patient misses dosing visits. For example, for IMCgp100 which is administered weekly, then a single dose interruption would be defined regardless of whether only 1 week was missed or 2 consecutive weeks dosing were missed.

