### 4.4 Secondary Endpoints

- Tolerability: Dose interruptions, reductions, and dose intensity of IMCgp100
- Assessments of anti-IMCgp100 antibody formation
- Date of death in all patients treated with IMCgp100

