**Table 6-2 Recommended Dose Modifications by Toxicity Grade for Study Medications**

Worst Toxicity NCI CTCAE v4.03 Grade	Recommended Dose Modifications
	
Management: Treat according to institutional practice which generally includes an anti-pruritic regimen (see grade 2 management above). In addition, corticosteroid treatment (oral or topical) can be considered for symptomatic rash that does not respond to anti-pruritic regimen. For topical regimens, refer to grade 2 management above).
 
Dose adjustments: If grade 3 rash observed with IMCgp100 resolves to NCI CTCAE grade <math>\leq 1</math> within 7 days, restart at the same dose. If grade 3 rash resolves to NCI CTCAE grade <math>\leq 1</math> in 7–21 days, restart with a reduction in the dose of IMCgp100, as discussed with the medical monitor.

Grade 4	
Any grade 4 rash, permanently discontinue IMCgp100.
 
Manage according to institutional practice, consultation with a dermatologist is recommended.
 
All study medications must be permanently discontinued.

Infusion Reactions	
Grade 1	
Administer medications for symptomatic relief as needed. Infusion interruption may be considered until resolution of the event (up to 4 hours). The infusion rate of the study medication may be decreased by 50%. If resolved with decreased rate of infusion, any subsequent infusions can be administered at the reduced rate.

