#### 9.6.1.4 Tolerability

Tolerability of study treatment will be assessed by summarizing the number of treatment dose interruptions and dose reductions. Reasons for dose interruptions and dose reductions will be listed by patient and summarized.

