3.3. Changes to Analysis from Protocol

The following are documented changes to analysis from protocol:

- Tables/Listings for change from baseline and shift tables are removed from the analysis for vital signs and ECG data. Note that vital signs will only be collected at baseline.

4. Planned Analyses

A final analysis after database lock is planned for this study.

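### SAP 13 drops dose-reduction counts from the tolerability endpoint without declaring it, its dose intensity leaves out the final weekly interval, and its relative dose intensity cannot see delay without a missed visit

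*SAP*

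**What the plan says.** Protocol 4.4 and Table 4-1 define the endpoint as "Tolerability: Dose interruptions, reductions, and dose intensity of IMCgp100". Protocol 9.6.1.4 asks for the number of both interruptions and reductions, and adds: "Reasons for dose interruptions and dose reductions will be listed by patient and summarized".

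SAP 13 says "Tolerability of study treatment will be assessed by summarizing the number of treatment dose interruptions", followed by "Reasons for dose interruptions will be listed". Reductions do not appear, and reasons are listed but no longer summarized. SAP 13.1 defines an interruption but not a reduction, although its note c on completed cycles says "Reduced doses are allowed, as per number of cycles started above". Reductions are foreseen in the protocol. For a grade 3 rash that takes 7 to 21 days to settle, Table 6-2 says "restart with a reduction in the dose of IMCgp100, as discussed with the medical monitor", and the text after that table ends treatment for patients who need more than 2 reductions. The only departure that SAP 3.3 declares is "Tables/Listings for change from baseline and shift tables are removed from the analysis for vital signs and ECG data".

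On exposure, SAP 13.1 takes duration as the last dose date minus the "date of first study drug administration in the rollover study + 1). Note that this calculation does not include any post dose rest period". Dose intensity is total actual dose divided by that duration, times 7. Planned dose intensity is total planned dose divided by the same duration, times 7, and RDI is the ratio of the two. Protocol 9.4 instead compares dose intensity with planned dose over planned duration.

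**The concern.** There are three separate problems with one endpoint.

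- **Reductions.** A component named in the protocol has no count, no definition and no summary of reasons in the SAP. The section meant for declaring changes is silent on it.
- **Dose intensity.** A weekly dose covers a week. Ending the clock on the day of the last dose counts n doses over about n − 1 weeks, so the result is always too high for on-time dosing.
- **RDI.** With one duration in both numerator and denominator, time drops out. A measure meant to show lateness as well as shortfall then shows only shortfall in dose.

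The study tests no hypothesis (SAP 6.5), so these descriptive summaries are the tolerability result. A patient early in the rollover who missed a dose, or had it lowered, can show a dose intensity close to or above the full weekly dose.

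**Working it through.** The documents give no exposure figure to reproduce, so the SAP formulas are applied directly.

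**Inputs.** Weekly dosing, 7-day interval (SAP 13.1). 50 mcg weekly, the maximum in Protocol Table 2-1, as illustration; the percentages do not depend on it. Visit window of ±7 days (Protocol 7.1, SAP 6.4). Planned dose summed over planned dosing visits, missed ones included (SAP 13.1, note d).

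**Dose intensity, n on-time doses of 50 mcg.** Duration = 7(n − 1) + 1 = 7n − 6 days. SAP dose intensity = 50n / (7n − 6) × 7. With the final interval, duration = 7n and the result is 50 for every n. The relative excess is 6 / (7n − 6).

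| Doses | SAP duration (days) | SAP dose intensity (mcg/week) | Excess |
|---|---|---|---|
| 1 | 1 | 350.0 | +600% |
| 4 | 22 | 63.6 | +27.3% |
| 8 | 50 | 56.0 | +12.0% |
| 13 | 85 | 53.5 | +7.1% |
| 18 | 120 | 52.5 | +5.0% |
| 52 | 358 | 50.8 | +1.7% |

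The one-dose row is the limiting case. The excess is 5% or more up to 18 doses.

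**Imperfect dosing.**

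- One missed dose (not the last) of 8: 350 / 50 × 7 = 49.0, against 350 / 56 × 7 = 43.75. SAP RDI is 350 / 400 = 87.5%, so RDI does show the miss.
- Four on-time doses at an illustrative 40 mcg (20% lower): 160 / 22 × 7 = 50.9, against 160 / 28 × 7 = 40.0. SAP RDI is 160 / 200 = 80%.

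**RDI.** SAP RDI = (actual / duration) / (planned / duration) = actual / planned. Take four full doses on Days 1, 11, 21 and 29 against scheduled Days 1, 8, 15 and 22. They are 0, 3, 6 and 7 days late, all in window, with no visit missed. Planned duration is taken as the scheduled time for the same doses; Protocol 9.4 does not define it.

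- SAP: (200 / 29) / (200 / 29) = 100%.
- Protocol 9.4, without the final interval: (200 / 29) / (200 / 22) = 22 / 29 = 75.9%.
- With the final interval in both durations: (200 / 35) / (200 / 28) = 80.0%.

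**How much delay can be hidden.** If windows are anchored to the original schedule, total hidden delay is at most 7 days and the true RDI is at least 7n / (7n + 7): 80.0% at 4 doses, 92.9% at 13, 96.3% at 26 and 98.1% at 52. If each late dose instead moves the later ones, delay accumulates. Twelve full doses 10 days apart still read 100% under the SAP. Under Protocol 9.4 they give 78 / 111 = 70.3%, or 84 / 117 = 71.8% with the final interval.

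**The case against.** The strongest reply has four parts.

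1. **Reductions.** SAP 8 leaves the content of tables to template shells that are not in the published documents, so a reduction table may exist there. In the visible text, only the grade 3 rash row of Table 6-2 prescribes a reduction. A lower dose agreed at rollover entry becomes the planned dose under note d, so it is not an on-study reduction. All of this is fair, but the SAP text still plans no count and declares no removal.
2. **Dose intensity.** Excluding the time after the last dose is stated openly, and Protocol 9.4 does not say whether the final interval counts. The effect cancels in RDI and is small at a year of dosing, which is where the long-term safety objective lies. This stands: it is a poor definition, not a breach of the protocol. Long treatment in the parent study does not remove it, because dose intensity is calculated from the first rollover dose.
3. **RDI.** The delay patterns are invented, since the documents give no data on actual spacing, and 75.9% leaves out the final interval; 80% is the consistent figure. SAP dose intensity does register the delay: 200 / 29 × 7 = 48.3, against 63.6 on time. These points limit the size of the problem. They do not restore the Protocol 9.4 definition, and that departure is also undeclared.
4. **Side effect of the repair.** With the planned weekly dose as denominator, in-window early dosing can exceed 100%. Doses on Days 1, 8, 15 and 20 give (200 / 26 × 7) / 50 = 107.7%. That is correct behaviour, because the drug was given faster than planned.

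**Conclusion.** The concern holds in all three parts, with unequal weight, and should be corrected.

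- The missing reduction count and the missing summary of reasons are an undeclared departure from Protocol 9.6.1.4. This is the strongest part. Reductions show only indirectly, through lower actual dose and RDI.
- Dose intensity is biased upward by 27% at 4 on-time doses, 12% at 8 and 1.7% at 52. It matters for patients with short rollover treatment.
- RDI is an undeclared change from Protocol 9.4 and cannot see delay that creates no missed visit. In the four-dose example it reads 100% where 80% is right. At 52 doses the hidden loss is at most 1.9 points (100 − 98.1) if windows are anchored to the original schedule, and more if delays accumulate.

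The RDI figures assume that planned duration means the scheduled time for the same doses, and they use illustrative dose dates.

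**What to change.** 1. **Reductions.** Add the number and percentage of patients with at least one reduction, and the number of reductions. Define a reduction as a lowered prescribed dose relative to the planned or previous dose, and keep it apart from an infusion that was only partly given. List and summarize reasons for interruptions, and for reductions where the eCRF collects them. If any of this is left out on purpose, declare it in SAP 3.3.
2. **Dose intensity.** For this calculation only, use last dose date − first dose date + 7 days. Leave the reported duration of treatment as it is.
3. **RDI.** Divide the corrected dose intensity by the planned weekly dose. The four-dose example then gives (200 / 35 × 7) / 50 = 80%.

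The cost is SAP wording, derivation code and one added table block. Actual dose, planned dose and dates are on the eCRF pages named in SAP 13.1, and Protocol 6.1 requires every dose change to be recorded. One item needs checking: the SAP mentions a reason field for omitted doses only, so whether one exists for reductions is not known from the documents.

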13.1.1. Missing Data Methods For Study Exposure Variables

Missing data for elements of certain study exposure variables will be handled as follows:

- The date of first study drug administration is not expected to be missing for any patients.
- If the date of last study drug administration is missing or partial, then the date will be taken instead from the Date of discontinuation on the *End of Treatment* page of the eCRF.

14. Efficacy Outcomes

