### 7.2.2 Discontinuation of Study Treatment

Patients may voluntarily discontinue from the study treatment for any reason at any time. If a patient decides to discontinue from the study treatment, the investigator should make every effort to determine the primary reason for this decision and record this information in the patient's chart and

on the appropriate eCRF pages. Other reasons for discontinuation of study treatment are outlined in [Section 6.6](#).

Patients will be considered withdrawn from treatment if they state an intention to withdraw, fail to return for visits, or become lost to follow-up for any other reason.

The investigator should discontinue study treatment for a given patient if he/she believes that continuation would be detrimental to the patient's well-being.

At the time patients discontinue study treatment, a visit should be scheduled as soon as possible, within 14 days of the last dose of study drug or within 14 days of the decision to permanently discontinue study treatment, at which time all of the assessments listed for the EOT visit will be performed ([Table 7-1](#)). If the decision to withdraw the patient occurs at a regularly scheduled visit, that visit may become the EOT visit rather than having the patient return for an additional visit. An end of treatment eCRF page should be completed, giving the date and reason for stopping the study treatment. End of treatment/premature withdrawal visit is not considered as the end of the study.

Patients who discontinue study treatment should NOT be considered withdrawn from the study. They should return for the assessments indicated in [Section 7](#) and [Table 7-1](#) and be followed for the 90-day Safety Follow-up Period at a minimum. If they fail to return for these assessments for unknown reasons, every effort (eg, telephone, email, postal letter) should be made to contact them. At this time, the reason for study completion should be recorded on the Study Disposition eCRF page.

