15.1. Adverse Events

Patients with multiple adverse events in the same category are counted only once in that category and those with adverse events in more than 1 category are counted once in each of those categories. Adverse Events (AEs) will be coded using Medical Dictionary for Regulatory Activities (MedDRA) central coding dictionary, using the latest version of MedDRA available at the time of coding for the reporting period.

Treatment-emergent adverse events (TEAEs) are defined as AEs that started or worsened in severity from the date of first dose of the rollover study (regardless of time) up until 90 days after the last dose of study drug of this rollover study.

See [APPENDIX 2](#) for handling of partial dates for AEs. In the case where it is not possible to define an AE as treatment-emergent or not, the AE will be classified by the worst case; i.e. treatment emergent.

An overall summary of number of patients within each of the categories described in the subsection below, will be provided as specified in the templates.

An AE Listing will include TEAEs and Non-TEAEs, including those from before the first dose in the parent study and post-treatment periods which will be flagged as such. Only TEAEs will be summarized.

AE Structure as Recorded in the eCRF:

AEs will be recorded in the eCRF such that any change in severity over the course of their duration will be recorded as a single record. The AE/SAE eCRF page collects ‘Initial Grade’ and ‘Most Extreme Grade’ but not the date of the severity grade change. No further manipulation post collection is required, and the AE/SAE data will be listed as recorded.

The definition of a treatment-emergent AE will be handled for AEs that change in severity over the course of their duration, by assuming that any AE that *might have worsened* in severity within the timeframe from the date of first dose of the rollover study (regardless of time) up until 90 days after the last dose of study drug, will be defined as treatment-emergent. A worsening severity is defined as changing from a less severe (lower) CTCAE grade to a more severe (higher) CTCAE grade. For example, if an AE started prior to date of first dose of the parent study but ended on or after date of first dose of the parent study (regardless of time), and the ‘Most Extreme Grade’ is more severe (higher) than the ‘Initial Grade’, then the AE is assumed to be treatment-emergent.

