		-If start date > study drug end date + 90, then not TEAE Note: If study drug end date is missing, then as long as the imputed start date ≥ study drug start date, then TEAE.
	Missing	Impute start date as earliest possible date (i.e. first day of month if day unknown or 1st January if day and month are unknown). Then, consider the following: -If start date ≤ study drug end date + 90, then TEAE -If start date > study drug end date + 90, then not TEAE Note: If study drug end date is missing, then as long as the imputed start date ≥ study drug start date, then TEAE.
Missing	Known	If stop date < study drug start date, then not TEAE If stop date ≥ study drug start date, then TEAE
	Partial	Impute stop date as latest possible date (i.e. last day of month if day unknown or 31st December if day and month are unknown), then: If stop date < study drug start date, then not TEAE If stop date ≥ study drug start date, then TEAE
	Missing	Assumed TEAE

Note: Study drug start date is the parent study first drug date.

ALGORITHM FOR PRIOR / CONCOMITANT MEDICATIONS:

START DATE	STOP DATE	ACTION
Known	Known	If stop date < study drug start date, assign as prior If stop date ≥ study drug start date and start date ≤ end of treatment, assign as concomitant If stop date ≥ study drug start date and start date > end of treatment, assign as post study
	Partial	Impute stop date as latest possible date (i.e. last day of month if day unknown or 31 st December if day and month are unknown), then: If stop date < study drug start date, assign as prior If stop date ≥ study drug start date and start date ≤ end of treatment, assign as concomitant If stop date ≥ study drug start date and start date > end of treatment, assign as post treatment
	Missing	If stop date is missing could never be assumed a prior medication If start date ≤ end of treatment, assign as concomitant If start date > end of treatment, assign as post treatment
Partial	Known	Impute start date as earliest possible date (i.e. first day of month if day unknown or 1 st January if day and month are unknown), then: If stop date < study drug start date, assign as prior If stop date ≥ study drug start date and start date ≤ end of treatment, assign as concomitant If stop date ≥ study drug start date and start date > end of treatment, assign as post treatment

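### SAP 13.1.1 replaces a missing last-dose date with the discontinuation date, which can overstate treatment duration and understate dose intensity when doses were held before discontinuation

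*SAP*

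**What the plan says.** SAP 13.1 (note g) gives the normal source: "The date of last study drug administration is taken from the latest" Dose end date on the eCRF. Duration of treatment is "date of last study drug administration – date of first study drug administration in the rollover study + 1", and the SAP adds that this leaves out any rest period after the dose. Dose intensity is total actual dose divided by duration, times 7. Planned dose is summed over planned visits, missed ones included, up to the last administration. Skipped doses with no later administration are treated as discontinuation, not as an interruption.

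SAP 13.1.1 opens with "Missing data for elements of certain study exposure variables will be handled as follows" and then gives the fallback: "If the date of last study drug administration is missing or partial, then the date will be taken instead from the Date of discontinuation". That field sits on the End of Treatment page. Nothing is tried before that date.

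Protocol 9.4 lists the date of last dose and the date of discontinuation as separate items. Protocol 7.2.2 times the End of Treatment visit "within 14 days of the last dose of study drug or within 14 days of the decision to permanently discontinue study treatment", so it too allows the two to differ.

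For adverse events with a partial onset date, SAP Appendix 2 has its own note: "If study drug end date is missing, then as long as the imputed start date ≥ study drug start date, then TEAE". SAP 15.1 says that where emergence cannot be decided, "the AE will be classified by the worst case; i.e. treatment emergent".

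**The concern.** The discontinuation date need not be close to the last infusion. Protocol Table 6-2 has doses held until recovery and states no maximum hold for other events of grade 3 or higher. A patient may therefore miss several weekly visits before treatment is formally stopped. Substituting the later date adds to duration the period that SAP 13.1 excludes, and it moves the cut-off for planned dose past visits that SAP 13.1 regards as following discontinuation. A partial date also loses its known month and year.

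At stake are duration (from the first rollover dose and from the first parent-study dose), dose intensity and possibly relative dose intensity. Dose intensity is part of the tolerability endpoint in Protocol 4.4. Patients with a missing date would be measured on a different basis from the rest.

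The secondary question is whether Appendix 2, when the drug end date is missing, can leave out of the treatment-emergent summary an event that it would include if the end date were known.

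**Working it through.** The documents contain no worked exposure figure to reproduce, so the SAP 13.1 formulas are applied directly.

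**Inputs from the documents.** Dosing is weekly (SAP 13.1) and the dose is 50 mcg (Protocol Table 2-1).

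**Assumptions, not in the documents.** The patient receives n consecutive weekly doses with none missed. Discontinuation is recorded g = 21 days after the last infusion.

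**Formulas.** True duration is T = 7(n − 1) + 1. With the fallback it becomes T + g. Dose intensity is 50n/T × 7, or 50n/(T + g) × 7 with the fallback. The percentage changes do not depend on the dose.

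| Doses | Duration, days | Change | Dose intensity, mcg/week | Change |
|---|---|---|---|---|
| 4 | 22 → 43 | +95.5% | 63.6 → 32.6 | −48.8% |
| 12 | 78 → 99 | +26.9% | 53.8 → 42.4 | −21.2% |
| 26 | 176 → 197 | +11.9% | 51.7 → 46.2 | −10.7% |
| 52 | 358 → 379 | +5.9% | 50.8 → 48.0 | −5.5% |

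For 12 doses: 7 × 11 + 1 = 78; 78 + 21 = 99; 600/78 × 7 = 53.8; 600/99 × 7 = 42.4.

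**Other gaps, 26 doses.** Gaps of 7, 14, 28 and 42 days change duration by +4.0, +8.0, +15.9 and +23.9%, and dose intensity by −3.8, −7.4, −13.7 and −19.3%. A gap of zero changes nothing.

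**Relative dose intensity.** Actual and planned dose intensity share the same duration, so it cancels and the ratio is actual dose over planned dose. For 12 doses the held visits fall on days 85, 92 and 99, and day 99 is the discontinuation day itself.
- All three counted as planned: 600/750 = 80%.
- Day 99 not counted: 600/700 = 85.7%.
- No held visit counted as planned: 600/600 = 100%.

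**Appendix 2, partial onset.** Suppose the onset could fall on or after drug start and the event's stop date does not precede drug start. The onset is imputed to the first day of the month, or to 1 January.
- Drug end date known: only the upper limit (end date + 90 days) is tested. An onset in the drug-start month counts as treatment-emergent.
- Drug end date missing: the note requires the imputed onset to be on or after drug start. An onset in the drug-start month passes only if drug start was the first of a month; a year-only onset in the drug-start year passes only if it was 1 January.

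If drug start is spread evenly over the year, the test fails in 1 − 12/365.25 = 96.7% of same-month cases and 1 − 1/365.25 = 99.7% of same-year, year-only cases. These are proportions within a narrow set of events, not rates of misclassified events.

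**The case against.** The strongest reply is that this is a last-resort rule that will seldom be used. Site staff give the infusions under supervision (Protocol 6.4.2), and missing values are queried (Protocol 10.4). The eCRF completion rule for the discontinuation date is not shown. The protocol says only that the page records the date and reason for stopping treatment, and if sites enter the last-dose date there is no error. The study aims at dosing beyond one year, where the effect is small, and no source supports a 21-day gap. All of this stands and limits the size of the point. It does not remove it: Protocol 9.4 treats the two dates as distinct, and a closer substitute is already collected.

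A reader might go further and infer that the 90-day adverse event window moves as well, ending 90 + 21 = 111 days after the true last dose. The documents do not support that. SAP 13.1.1 is confined to exposure variables, and nothing in SAP 15, 15.1 or Appendix 2 carries its date across. For a missing end date, Appendix 2 applies no 90-day limit at all; for a partial end date it is silent.

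A reader might likewise infer that the split between concomitant and post-treatment medication shifts. SAP 12 words the split by last dose, but the Appendix 2 algorithm uses end of treatment, and neither refers to 13.1.1.

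On Appendix 2, two objections hold in part. As printed, drug start there is the first parent-study dose, so the stricter test is a problem for rollover events once that is aligned with SAP 15.1. The note also never says that a failing event is not treatment-emergent, so the worst-case rule might be held to rescue it. A programmer should not have to choose between the two.

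**Conclusion.** The point holds in a limited form and is minor. Applied as written, SAP 13.1.1 can overstate duration and understate dose intensity for a patient whose last-dose date is missing or partial and whose discontinuation was recorded after held doses. For an assumed 21-day gap the changes run from +27% and −21% at 12 doses to +6% and −5.5% at 52. For 12 doses, relative dose intensity is 80–86% if held visits count as planned and 100% otherwise. The gap length and the uninterrupted course are assumptions. The documents do not show how many patients would be affected; few is a reasonable expectation. It would go too far to say that exposure is wrong for every patient handled by the rule.

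The Appendix 2 inconsistency is visible in the text and runs against the worst-case rule in SAP 15.1. Its effect on rollover events depends on first correcting the definition of drug start.

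**What to change.** **SAP 13.1.1.** If the dose end date is missing or partial:
1. Use the Dose start date of the last record with an actual dose above zero.
2. If that is missing, use the date of that dosing visit.
3. Only if both are missing, use the discontinuation date, kept within any known month and year of a partial date. Flag these patients in the exposure listing.

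**SAP Appendix 2.** Once drug start is aligned with the first rollover dose, change the note in the partial-onset rows: when the drug end date is missing, classify the event as treatment-emergent if its stop date is missing or falls on or after drug start. Keep the existing test that excludes events whose stop date precedes drug start. An unconditional note could override that test and bring in events that had resolved before the first dose.

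**Which end date.** State which drug end date treatment-emergence classification uses, including when that date is partial.

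The cost is a few sentences in the SAP and the matching program changes. No new data are needed.
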